### Analysis of Primary Efficacy and Safety Endpoints

Spearman correlation coefficient will be obtained between mean change from baseline in CFS score at visit X and SANDE symptoms score at each visit X+i for each FAS population in Period 1, Period 2, and entire study. For Period 1, visit X includes Day1, Month 3, Month 6, Month 9 and Month 12, and i is from 0 (Day 1) up to 4 (Month 12). For Period 2, X includes Month 12, Month 15, Month 18, Month 21, Month 24, Month 27, Month 30, Month 33, and Month 36, and i is from 0 (Month 12) up to 8 (Month 36). Correlation coefficient will be analized by treatment group. For entire study, visit X includes all the scheduled visits from Day 1 to Month 36, and i is from 0 (Day1) up to 12 (Month 36). Missing data will not be imputed.

The incident rate of ocular surface complications (defined as corneal ulceration, corneal perforation, loss of visual acuity, and ocular infection) will be estimated with its 95% CI for each safety population in Period 1, Period 2, and the entire study. The analysis for safety population in Period 2 will be conducted by treatment group. These rates will be compared to existing epidemiologic rates in a comparable population. Time to onset and time to resolution of the ocular complications will also be summarized.

Missing data will not be imputed.

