### 4. INTRODUCTION

Since the 2017 International Dry Eye Workshop (DEWS), the term dry eye disease (DED), also known as keratoconjunctivitis sicca, describes "a multifactorial disease of the ocular surface characterized by a loss of homeostasis of the tear film, and accompanied by ocular symptoms, in which tear film instability and hyperosmolarity, ocular surface inflammation and damage, and neurosensory abnormalities play etiological roles (DEWS 2017a)". The prevalence of DED ranges from 5% to 50% (DEWS 2017b).

Any abnormality of the ocular surface can trigger disequilibrium of the ocular surface integrity and leads to DED (Labetoulle 2013). This results in a vicious circle (Baudouin 2013) with as many ways to enter as there are causes of destabilization of the ocular surface (Baudouin 2007). The pathogenesis of DED is not fully understood; however inflammation has a prominent role in the development and amplification of the signs and symptoms of DED (Stevenson 2012). DED prognosis shows considerable variance, depending upon the severity of the condition and the severity of the underlying pathology. There are very few approved pharmacological treatments for DED in the world, and patients report using artificial tears on a frequent basis (Kymionis 2008). Most patients have mild-to-moderate complaints and can be treated symptomatically with lubricants for long periods of time.

Patients with more severe conditions of DED such as those with severe keratitis (or Sjögren's syndrome) represent a group of patients with worse prognosis (AAO 2013) and in need of more effective treatments (Asbell 2010). These DED patients with severe keratitis are trapped in a vicious cycle of inflammation and ocular surface injury with the risk of complications such as keratinization of the ocular surface, the occurrence of corneal scarring, a thinning or corneal neovascularization, sterile or microbial corneal ulcerations with a risk of perforation of the cornea and possible vision loss (AAO 2013). Even though epidemiological data on DED long term evolution is rare, Petroutsos et al., 1992 showed, after a 6-year follow-up, a lower-bound of the estimate of the complication rate of 4% in severe patients (Petroutsos 1992). Thus for these severe diseases which need long-term treatment, clinical guidelines recommend using anti-inflammatory agents such as ciclosporin A (CsA) when lubricants are inadequate (DEWS 2017d).

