#### 13.1.1. Sample Size

This sample size of this study is not planned from a formal sample size calculation since formal statistical hypothesis testing will not be performed for the primary endpoints. In this study, we plan to enroll 350 subjects. Of the 350 subjects, it is estimated that approximately 70% (245 subjects) would become markedly improved in CFS after Month 12 and enter the Period 2 (Double-masked randomised period), based on Santen previous IKERVIS studies. With a 3:2 randomization allocation ratio, a sample size of 147 for IKERVIS® and 98 for Vehicle will allow to detect a difference of 0.4 or more in CFS score with 80% power assuming the standard deviation of the difference is 1.10.

Petroutsos *et al.* (1992) showed that after 6 years of follow-up on DED patients, a lower-bound of the estimated complication rate was 4% in severe DED patients. In the current study, 350 subjects treated with IKERVIS® for at least one year would have 95% power to detect at least one ocular complication that occurs at 1% rate with type I error rate of 0.05.

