# 13.4. Analysis of Primary Endpoints

Spearman correlation coefficient and p-values will be obtatined for the correlation analysis between mean change from baseline in CFS score at visit X and symptoms score at each visit X+i for each FAS population in Period 1, Period 2 and entire study. For Period 1, visit X includes Day1, Month 3, Month 6, Month 9 and Month 12, and i is from 0 (Day 1) up to 4 (Month 12). For Period 2, X includes Month 12, Month 15, Month 18, Month 21, Month 24, Month 27, Month 30, Month 33, and Month 36, and i is from 0 (Month 12) up to 8 (Month 36). Correlation coefficient will be analized by treatment group. For entire study, visit X includes all the scheduled visits from Day 1 to Month 36, and i is from 0 (Day1) up to 12 (Month 36). Missing data will not be imputed.

The incident rate of ocular surface complications (defined as corneal ulceration, corneal perforation, loss of visual acuity, and ocular infection) will be estimated with its 95% CI for each safety population in Period 2, and the entire study. The analysis for safety population in Period 2 will be conducted by treatment group. The incident rates will be compared to existing epidemiologic rates in a comparable population. Time to onset and time to resolution of the ocular complications will also be summarized. Missing data will not be imputed.

Subgroup analysis by randomization stratification factor will be conducted to test the homogeneity of treatment effects in Period 2.

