3. STUDY DESIGN

3.1. General Study Design

This is a phase IIIb, prospective, interventional, multicentre, three-year study to explore the long-term evolution of sign and symptoms, and occurrence of complications in dry eye disease subjects with severe keratitis receiving IKERVIS® (1mg/ml ciclosporin) eye drops. All enrolled subjects will enter a period of 12 months of treatment (Period 1) with open-label IKERVIS® treatment [once daily (QD) into the affected eye(s) at bedtime]. At Month 12 visit, markedly improved subjects will continue the study for an additional 24 months randomized, double-masked treatment period (Period 2) to receive either IKERVIS® QD or vehicle QD (at a ratio of 3:2), Figure 1.

Figure 1. Study Design Diagram

IKERVIS will be used with AT (same AT for all patients) up to 6 times per day

Markedly improved subjects are defined as subjects having a corneal fluorescein staining (CFS) score improvement from baseline of 2 grades or more on the modified Oxford scale [unless if the subject had a CFS score of 5 at baseline, the improvement in CFS has to be 3 grades or more] in the study eye. Subjects who are not markedly improved at Month 12 based on the above definition will be terminated from the study.

This study will be conducted in about 36 sites located in European and non-European countries.

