3.3. Sample Size Determination

The sample size of this study is not planned from a formal sample size calculation since formal statistical hypothesis testing will not be performed for the primary endpoints. In this study, we plan to enroll 350 subjects. Of the 350 subjects, it is estimated that approximately 70% (245 subjects) would become markedly improved in CFS after Month 12 and enter the Period 2 (double-masked randomized period), based on Santen previous IKERVIS studies. With a 3:2 randomization allocation ratio, a sample size of 147 for IKERVIS® and 98 for Vehicle will allow us to detect a difference of 0.4 or more in CFS score with 80% power assuming the standard deviation of the difference is 1.10.

Petroutsos *et al.* (1992) showed that after 6 years of follow-up on DED subjects, a lower-bound of the estimated complication rate was 4% in severe DED subjects. In the current study, 350 subjects treated with IKERVIS® for at least one year would have 95% power to detect at least one ocular complication that occurs at 1% rate with type I error rate of 0.05.

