6. ANALYSIS POPULATION

Analysis populations defined for each analysis period are as follows.

For Period 1:

- The FAS (Full Analysis Set) Period 1 population consists of all enrolled subjects who received at least one dose of the study medication and had at least one post-baseline sign or symptom assessment of the study eye during Period 1. This will be the population used for efficacy analyses of Period 1.
- The **PPS** (**Per-Protocol Set**) **Period 1** will be a subset of FAS, restricted to the subjects who fulfill the protocol in the terms of the eligibility, interventions, and outcome assessment. It will be the analysis population for some sensitivity analyses.
- The **Safety Population Period 1** consists of all subjects enrolled in Period 1 who received at least one dose of the study medication and for whom any follow-up information is available. It will be the analysis population for safety analyses to be performed with subjects as treated.
- The **Sjögren Patients Population** consists of subjects who were known to have diagnostic status of the Sjögren disease based on the medical history obtained at baseline.
- The **Subjects Markedly Improved during Period 1** are defined as FAS subjects who achieve CFS score improvement from baseline of 2 grades or more (unless if the subject had a CFS score of 5 at baseline, the improvement in CFS has to be 3 grades or more) at anytime during Period 1.

For Period 2 and Entire Study:

- The FAS Period 2 (or FAS Entire Study) population consists of all randomized subjects who received at least one dose of the double-masked study medication and had at least one post-Month 12 sign or symptom assessment of the study eye during Period 2. This will be the population used for efficacy analyses.
- The **PPS Period 2 (or PPS Entire Study)** will be a subset of FAS Period 2, restricted to the subjects who fulfill the protocol in the terms of the eligibility, interventions, and outcome assessment. It will be the analysis population for some sensitivity analyses.
- The Safety Population Period 2 (or Safety Population Entire Study) consists of all subjects randomized in Period 2 who received at least one dose of the double-masked study medication and for whom any follow-up information is available in Period 2. It will be the analysis population for safety analyses to be performed with subjects as treated.

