9.1. Analysis of Primary Safety Endpoint

The primary safety endpoint for this study is the incidence rate and time-to-onset of ocular surface complications, which include corneal ulceration, corneal perforation, loss of visual acuity, or ocular infection. Missing data will not be imputed.

The ocular surface complications incidence rate will be tabulated using frequency (n) and percentage (%) at Month 1-12, Month 13-24, Month 25-36 and for overall period 2 (Month 13-36). Month 1-12 incidence rate will be summarized for Period 1 Safety population. Month 13-

24, Month 25-36, and Month 13-36 (overall period 2) summaries will be conducted for Period 2 Safety population. The relative risk of the ocular surface complications incidence rate between the two treatment groups will be assessed at Month 13-24, Month 25-36 and Month 13-36 by producing odds ratio and its 2-sided 95% exact confidence interval.

For entire study analysis, the ocular surface complications incidence rate of IKERVIS group (a treatment group with IKERVIS during period) at Month 36 (1-36) will be compared to the existing epidemiologic rate in a comparable population, which was 4% based on results published by Petroutsos *et al.* (1992). The ocular surface complications incidence rate at Month 36 will be compared. This will be done using the Safety population Entire Study. Binomial proportions will be compared using SAS procedure PROC FREQ with binomial options.

The relative risk of the two treatment groups in terms of the time-to-first-onset of ocular surface complications (first event of each subject) will be assessed by producing the hazard ratio and its 2-sided 95% confidence interval if enough events are observed to make the analysis possible for period 2 (double masked period). The estimated hazard ratio and 95% CI will be obtained from a Cox proportional hazards model with treatment group as a covariate and region as stratification factor. Survival functions will be estimated using the Kaplan-Meier method, and Log-Rank test will be conducted to calculate nominal p-value.

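### SAP 9.1 tests the 3-year IKERVIS complication proportion against a fixed 4% that the documents elsewhere call a 6-year lower bound, in a set limited to patients randomised after marked improvement

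*SAP*

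**What the plan says.** SAP 9.1 (Analysis of Primary Safety Endpoint) takes the proportion of the IKERVIS group with an ocular surface complication over Months 1-36. It says that this "will be compared to the existing epidemiologic rate in a comparable population, which was 4% based on results published by" the authors of a 1992 paper. The set is the Safety Population Entire Study and the tool is PROC FREQ with binomial options. No alpha, sidedness or decision rule is given for this comparison.

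The same 4% is described three times elsewhere:

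- Protocol 4 (Introduction): "after a 6-year follow-up, a lower-bound of the estimate of the complication rate of 4% in severe patients".
- Protocol 13.1.1: "after 6 years of follow-up on DED patients, a lower-bound of the estimated complication rate was 4% in severe DED patients".
- SAP 3.3: "after 6 years of follow-up on DED subjects, a lower-bound of the estimated complication rate was 4% in severe DED subjects".

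SAP 6 defines the Safety Population Entire Study as the set that "consists of all subjects randomized in Period 2 who received at least one dose of the double-masked study medication" and has Period 2 follow-up. SAP 3.1 states who never gets that far: "Subjects who are not markedly improved at Month 12 based on the above definition will be terminated from the study". The protocol's own entire-study safety population (Synopsis and 13.2) is likewise limited to markedly improved patients randomised to IKERVIS.

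The protocol commits to a historical comparison without naming a value or a test at that point. The synopsis says "These rates will be compared to existing epidemiologic rates in a comparable population" and lists Period 1 among the rates. Section 13.4 says "The incident rates will be compared to existing epidemiologic rates in a comparable population" but lists only Period 2 and the entire study.

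**The concern.** A one-sample binomial comparison treats its reference value as known, and as describing the same events, over the same time, in the same kind of patient. SAP 9.1 drops both qualifiers that the documents attach to the 4%: the 6 years, and the fact that it is a lower bound. It then calls the source population comparable, although the trial set is conditioned on what happened during the first 12 of the 36 months being counted.

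There is also a question of event definition. The title of the cited source in SAP 11 concerns sterile corneal ulcers. The trial endpoint (SAP 4.4.1.1) is a composite of corneal ulceration, corneal perforation, loss of visual acuity and ocular infection. The documents say only that the historical figure is a complication rate.

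This is the planned historical comparison for a primary safety endpoint. A report could state that complications under IKERVIS were lower than, or no different from, the epidemiologic rate when the result reflects only the choice of benchmark and of patients.

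**Working it through.** **Can the 4% be reproduced?** No. The documents give no numerator, denominator or person-time for it, and do not say whether it is cumulative. What follows sets the descriptions side by side and then illustrates under stated assumptions.

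**Side by side**

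| | Trial proportion (SAP 9.1) | Historical 4% |
|---|---|---|
| Time | Months 1-36 | 6 years of follow-up |
| Kind of figure | estimate | lower bound |
| Patients | improved at Month 12, then randomised | severe DED |
| Events | four-part composite | complication rate; cited title names sterile corneal ulcers |

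**Selection.** SAP 3.3 expects 350 × 0.70 = 245 patients in Period 2, of whom 245 × 3/5 = 147 on IKERVIS. So 350 − 245 = 105 (30%) are expected never to be randomised. A Period 1 complication enters the 1-36 rate only if the patient stayed, was markedly improved at Month 12 and was randomised. The 98 patients expected on vehicle are absent from the IKERVIS rate by randomisation, which is not selective.

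**Illustration: time mismatch.** Assumptions, none confirmed by the documents: the 4% is a 6-year per-patient cumulative risk; the hazard is constant; the source counted the same events; two-sided 0.05; 147 patients all followed to Month 36.

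1. Three-year equivalent: 1 − (1 − 0.04)^(3/6) = 0.0202. Expected patients with an event: 147 × 0.0202 = 2.97, against 147 × 0.04 = 5.88 at the tested value.
2. Lower cut-off against 4%: P(X ≤ 1) = 0.96^147 + 147 × 0.04 × 0.96^146 = 0.0176, below 0.025. Two events give a doubled-tail p of 0.128. A nominal result of lower than 4% therefore needs 0 or 1 event; exact and asymptotic cut-offs agree.
3. Chance of that result when the true 3-year risk is 0.0202: 0.9798^147 + 147 × 0.0202 × 0.9798^146 = 0.0498 + 0.1508 = 0.2006. The hazard here equals the assumed historical one, so there is no drug effect. Against a benchmark of 2.02%, even 0 events in 147 would give p = 0.0995.

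**Sensitivity of the 20%**

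| True 6-year risk | 3-year risk | P(0 or 1 event), n = 147 |
|---|---|---|
| 4% | 2.02% | 20.1% |
| 6% | 3.05% | 6.0% |
| 8% | 4.08% | 1.6% |
| 10% | 5.13% | 0.4% |

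It also depends on the exact number analysed. At a 3-year risk of 2.02%, the exact test gives 23.4% at n = 137 (cut-off 1 event) but 6.2% at n = 136 (cut-off 0). If the 4% were instead an annual risk, the 3-year value would be 1 − 0.96^3 = 11.5% and the mismatch would run the other way.

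**The case against.** The strongest reply is that the study is exploratory (SAP 5.4) and has no hypotheses for primary or secondary endpoints (Protocol 13.1.2). SAP 9.1 states no decision rule for the 4% comparison, so a verdict of lower than 4% is inferred. SAP 3.3 already carries both qualifiers. The Month 1-12 rate is tabulated for the full Period 1 Safety population, and between-treatment conclusions can rest on the randomised Period 2 comparison. All of this is true and limits the seriousness, but none of it changes the comparison that 9.1 specifies.

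Three stronger readings are tempting and are not supported.

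- A reader might infer that the comparison is tilted towards IKERVIS. A 6-year reference against 3 years does so only if the 4% is cumulative, which the documents never say. A lower bound used as the rate works the other way.
- A reader might infer that leaving out patients who did not improve lowers the rate. They leave the denominator too, so at equal risk the proportion is unchanged. The documents give no risk contrast. The selection undermines the claim of comparability but does not establish a direction.
- A reader might take the fixed 4% for an undeclared departure from the protocol. Protocol 13.1 leaves analysis details to the SAP, the protocol commits to an epidemiologic comparison, and 4% is the only historical complication rate it cites. The restriction to randomised improvers also stands in the protocol. Naming the value and procedure is fairly read as elaboration.

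**Conclusion.** The point holds. SAP 9.1 uses as a fixed, comparable 3-year reference a figure that the same SAP calls a lower bound after 6 years. It applies that figure to a set from which about 30% of enrolled patients are expected to be absent for reasons tied to outcome or early exit. These mismatches stand on the documents' wording alone and need no assumption. The possible difference in events counted rests on the cited title and needs checking against the source.

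The size is uncertain. The 20% is the extreme case, with the true risk exactly at the quoted lower bound, and it depends on every assumption listed. If the source counted only ulcers, so that the trial's wider composite captured more events, 0 or 1 event would be less likely still. The net direction of bias cannot be determined.

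It would go too far to say that the observed rate has no meaning: an estimate with its interval beside a properly labelled historical figure can be read with caution. The risk is a misleading statement in the report on a primary safety endpoint, not a failed formal test. This should be fixed before the analysis. The randomised Period 2 comparison in 9.1 is unaffected.

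**What to change.** In SAP 9.1, replace the binomial test against a fixed 4% with a descriptive comparison, which still meets the protocol's commitment:

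- Report the IKERVIS rate of first complication per 100 patient-years with an exact 95% CI, or a 3-year Kaplan-Meier estimate with 95% CI. Either handles unequal follow-up; a crude proportion counts patients who leave without an event as event-free.
- Show the historical figure beside it, labelled as a 6-year lower bound. Rescale it to 3 years or to patient-years only after the sponsor has confirmed from the source what the 4% measures and which complications it counts.
- Remove the claim of a comparable population, or state the Month 12 selection next to it. Person-time does not remove that selection.
- Print the already planned Month 1-12 rate for the full Period 1 Safety population alongside. That set is not selected on improvement, and the synopsis already lists Period 1 among the rates to be compared.

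Cost: a rewritten paragraph in 9.1, one rate table and one check of the cited source; no new data. The downside is the loss of a nominal p-value against history, and a wide interval. For example, 3 events in 147 × 3 = 441 patient-years (no dropout, person-time not cut at the event) give 0.68 per 100 patient-years, exact Poisson 95% CI 0.14 to 1.99.

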2. STUDY OBJECTIVES AND ENDPOINTS

2.1. Objectives

The primary objectives of this study are:

- To evaluate the long-term efficacy of a continuous treatment of IKERVIS® (1mg/mL ciclosporin) eye drops in adult dry eye disease (DED) subjects with severe keratitis on corneal sign and DED symptoms, and to estimate the lag time (if any) to improvement in symptoms (if any).
- To assess the ocular surface complications (defined as corneal ulceration, corneal perforation, loss of visual acuity, and ocular infection) over the three-year study period.

The secondary objectives of this study are:

- To evaluate the efficacy parameters (signs and symptoms), the ocular surface complications, and the quality of life over treatment Periods 1 and 2.
- For 12-month markedly improved subjects, to evaluate and compare signs and symptoms evolution in IKERVIS® group versus Vehicle group during the randomised period of the study (Period 2).
- To evaluate the safety and tolerability of IKERVIS® (1mg/mL ciclosporin) eye drops treatment over the three-year study period.

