2.2. Endpoints

2.2.1. Primary Efficacy and Safety Endpoints

- The correlation between change from baseline in CFS score and SANDE symptoms score at each visit, and cross correlation of sign at visit X versus symptoms at visit X+i (i starting from 0), if any.
- Incident rate of ocular surface complications (defined as corneal ulceration, corneal perforation, loss of visual acuity and ocular infection
- Time to onset of ocular surface complications

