5.2. Handling of Missing Data

No imputation for missing data will be performed on any efficacy and safety endpoints. Unless specified otherwise, descriptive summaries will be based on observed cases.

Completely or partially missing onset and resolution dates for AEs, Concomitant Medications (CM), and Medical History (MH) will be imputed in a conservative fashion as follows:

Incomplete Adverse Event Onset Date

- 1. Year imputation
 - o If *year* is missing (or AE onset date is completely missing), then the onset date will not be imputed.
- 2. Month imputation
 - o If *year* is not missing but *month* is missing, then:

- If *year* = year of first study dose date, then set the *month* and *day* to the day and month of first study dose
- Else if $year \neq year$ of first study dose: set *month* to January

3. Day imputation

- o If day is missing (month and year not missing), then:
 - If year = year and month = month of first study dose, then set day to day of first study dose
 - Else if $year \neq year$ and $month \neq month$ of first study dose, then set day to first day of the month in the year

Incomplete Adverse Event Resolution Date

Do not impute if any resolution date is missing.

If the duration of AE is needed, the following approach may be considered:

- o If year is missing (or AE resolution date is completely missing): do not impute
- o If *year* is not missing but *month* and *day* are missing: impute December 31st for missing *month* and *day*
- o If *year* and *day* are not missing but *month* is missing: impute December for missing *month*
- o If *year* and *month* are not missing but *day* is missing: impute last day of the *month* for missing *day*.

Incomplete CM or MH Onset Date

- 1. If year is missing (or CM/MH onset date is completely missing), do not impute
- 2. If *year* is not missing but *month* and *day* are missing, impute January 1st for missing *month* and *day*
- 3. If year and day are not missing but month is missing, impute January for missing month
- 4. If year and month are not missing but day is missing, impute 01 for missing day

Incomplete CM or MH Resolution Date

- 1. If a resolution date is completely missing, do not impute.
- 2. If year is not missing but month and day are missing, use the last day of the year to impute the missing month and date parts of the resolution date.

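### The only Month 1-36 complication rate, the one compared with 4%, is a crude proportion in Month-12 responders randomised to IKERVIS; no patient-year or censored three-year estimate in all treated patients is specified

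*SAP*

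**What the plan says.** The second primary objective (SAP 2.1) is "To assess the ocular surface complications (defined as corneal ulceration, corneal perforation, loss of visual acuity, and ocular infection) over the three-year study period". The primary safety endpoints in SAP 2.2.1 are the incidence rate and "Time to onset of ocular surface complications".

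SAP 9.1 sets out three pieces of analysis:

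- **By window.** Counts and percentages for Months 1-12, 13-24, 25-36 and 13-36. For the first window, "Month 1-12 incidence rate will be summarized for Period 1 Safety population". The other three use the Period 2 Safety population.
- **Entire study.** One Month 1-36 rate, for the IKERVIS group, compared with 4% from a study published in 1992. "This will be done using the Safety population Entire Study". The method is given as "Binomial proportions will be compared using SAS procedure PROC FREQ with binomial options".
- **Time to first onset.** A Cox model, Kaplan-Meier curves and a log-rank test, in the paragraph that compares the two arms in Period 2.

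SAP 6 defines the population for the second piece: "The Safety Population Period 2 (or Safety Population Entire Study) consists of all subjects randomized in Period 2 who received at least one dose" of masked medication, with some follow-up in Period 2. Only markedly improved patients are randomised. SAP 3.1 adds: "Subjects who are not markedly improved at Month 12 based on the above definition will be terminated from the study".

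The protocol (13.2, entire study) also restricts this safety population to markedly improved patients randomised to IKERVIS. The protocol synopsis and section 13.4 promise a 95% CI for the rate and a summary of time to onset, without naming a method that handles censoring.

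**The concern.** The three-year figure starts counting at Day 1, but a patient belongs to its base only after reaching Month 12 as a responder and being randomised to IKERVIS. Two groups with a first year on IKERVIS therefore fall outside it:

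- Patients who leave in year 1 or are not markedly improved at Month 12. This is a selection on outcome, and its effect on the rate could go either way.
- Patients randomised to vehicle. They are left out by chance, so this costs precision only.

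A second question is early exit from Period 2. If every patient in the named population stays in the denominator, someone who leaves before any event counts as event-free to Month 36.

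At stake is what the answer to a primary objective describes. The objective speaks of the three-year study period in patients with severe keratitis. The single three-year figure describes those who did well on treatment for a year, and it is the figure set against an external rate. No person-time rate is specified anywhere. SAP 7.7 summarises exposure for everyone who received IKERVIS, but does not link it to complications.

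**Working it through.** **Planned numbers (SAP 3.3), reproduced.** 350 × 0.70 = 245 randomised. 245 × 3/5 = 147 IKERVIS and 245 × 2/5 = 98 vehicle. 350 − 245 = 105 do not enter Period 2. The Month 1-36 base is 147/350 = 42% of treated patients.

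**IKERVIS patient-years, ignoring dropout in Period 2.**
- In the three-year figure: 147 × 3 = 441.
- Outside it: 98 × 1 + 105 × 1 = 203. Total 441 + 203 = 644. Share outside: 203/644 = 32%.
- If the 105 average half a year (assumed): 98 + 52.5 = 150.5 outside, of 591.5. Share: 25%.

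**Expected first events.** The documents give no event rate for this trial. For illustration, assume a 36-month risk of 4% with constant hazard.
- One-year risk p = 1 − 0.96^(1/3) = 0.01352; hazard h = −ln(1 − p) = 0.01361 per year.
- In the figure: 147 × 0.04 = 5.88.
- Outside: 105p = 1.42 and 98p = 1.32, together 2.74.
- Total 8.62, so about 2.7 of 8.6 events lie outside.

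**Early exit in Period 2.** The documents give no dropout figure. SAP 9.1 names a population but states no denominator rule, and SAP 5.2 says "Unless specified otherwise, descriptive summaries will be based on observed cases". This step therefore holds only if the whole named population is the base. With dropout q per year, let d = −ln(1 − q) and r = h/(h + d) × (1 − e^(−2(h + d))). The proportion reads 1 − (1 − p)(1 − r).

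| Assumed dropout per year | Proportion reads (true 4%) |
|---|---|
| 5% | 3.87% |
| 10% | 3.74% |
| 20% | 3.49% |

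Sampling error is larger: 6/147 = 4.1%, exact 95% CI 1.5% to 8.7%.

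**What an all-treated estimate adds in precision.** Exact Poisson rates per 100 patient-years: 6/441 = 1.36 (0.50 to 2.96); 9/644 = 1.40 (0.64 to 2.65). At 4% with no dropout, the standard error is 1.62 points for the crude proportion and 1.45 for Kaplan-Meier.

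**How much selection it removes.** Let the 30% who do not respond have k times the responder hazard throughout (assumed), with responders at 4% over 36 months.
- Year-1 risk in all treated: y1 = 0.7p + 0.3(1 − (1 − p)^k).
- Kaplan-Meier: 1 − (1 − y1)(1 − p)².
- All-comer risk: 0.7 × 0.04 + 0.3(1 − 0.96^k).

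| k | Planned proportion | Kaplan-Meier, all treated | All-comer risk | Gap closed |
|---|---|---|---|---|
| 2 | 4.0% | 4.4% | 5.2% | 34% |
| 0.5 | 4.0% | 3.8% | 3.4% | 33% |

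**The case against.** The restriction is a declared choice, made in both protocol and SAP. Non-responders stop at Month 12, so three years of continuous IKERVIS exist only in the randomised IKERVIS arm, and a crude risk there is a coherent quantity. The study is exploratory, and protocol 13.1.2 sets no hypotheses for the primary and secondary endpoints. A pooled estimate would be imperfect too: it censors non-responders at Month 12 because of their corneal status, which may be informative, and it joins an all-comer first year to responder-only years 2 and 3. All of this stands. It is why the proportion should be kept and why the Kaplan-Meier estimate can be supportive only. It does not explain why the three-year objective should have no exposure-adjusted answer when the dates are already collected.

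Four stronger readings are tempting, and the documents do not support them:

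- *Year-1 complications in non-responders are lost.* They are not; the Month 1-12 table covers all treated patients.
- *The three-year rate is biased low.* The direction of the responder selection cannot be known from the documents, and the dropout effect depends on an unstated denominator.
- *Time to onset over the whole study is unplanned.* The protocol promises a summary. What is limited to Period 2 is the SAP's set of named survival methods.
- *The same denominator question undermines the Month 25-36 odds ratio.* Too few events are expected in that window for this to carry weight.

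**Conclusion.** The point holds as a matter of scope and completeness. The one Month 1-36 figure describes Month-12 responders randomised to IKERVIS, and a complication in a patient who left in year 1 or did not respond cannot enter it. Between 25% and 32% of planned IKERVIS patient-years do not feed it, depending on how early the 105 leave. No person-time or censored estimate for Months 1-36 is specified.

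The patient-year shares rest on the planned sizes in SAP 3.3. The event counts, dropout shifts and hazard multiples are illustrations under stated assumptions. Any dropout effect (4% reading 3.9% to 3.5%) is smaller than sampling error.

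Severity is minor to moderate: the population is declared and no hypothesis depends on it, but the figure answers a primary objective and is the one compared with an outside rate.

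**What to change.** Keep the Month 1-36 proportion. State in its table title and in the conclusion that it applies to Month-12 responders randomised to IKERVIS, and state its denominator. Add to SAP 9.1:

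> In the Safety Population Period 1, the first ocular surface complication on IKERVIS will be summarised as events per 100 IKERVIS patient-years with exact Poisson 95% CI, overall and for Months 1-12 and 13-36. Time starts at the Period 1 treatment start date. Patients without an event are censored at the first vehicle dose (vehicle arm) or at the last study visit. The 36-month Kaplan-Meier cumulative incidence with 95% CI will be presented as supportive. Non-responders are censored at Month 12 because of their corneal status, which may be informative, so this estimate joins an all-comer first year to responder-only years 2 and 3. It reduces but does not remove selection.

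Also show the Month 1-12 rate with 95% CI by Month-12 status: randomised, not markedly improved, left earlier.

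The cost is a patient-year table, a Kaplan-Meier table or figure, a by-status table and a title change. No new data are needed. Censoring should use the last study visit, because AEs are collected to that visit (SAP 4.4.1) while the treatment end date is set one day before it (SAP 4.1.2). The by-status rates will be imprecise: 350 × 0.01352 = 4.7 expected events in total at the assumed rate. The change does not cure a separate mismatch: SAP 3.3 describes the 4% as a lower bound after 6 years, which under constant hazard is 1 − 0.96^0.5 = 2.0% at 36 months.
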